4.2.2. Visit 2 (*Month 2*) +/- 4 days

Subjects will continue to take BLI400 daily and will return to the clinic for Visit 2 (Day 60). Vital signs (see [section 4.1](#) for details) and ECGs will be recorded. Study personnel will weigh returned bottles and count rescue bisacodyl for accountability purposes. Subjects will be queried for any adverse events or changes to their concomitant medications. Subjects will complete the PAC-QOL and PAC-SYM questionnaires. Samples for chemistry, hematology and urinalysis will be repeated as outlined in [Section 4.1](#). Subjects will be dispensed 2 new bottles of study medication. Subjects will be instructed to return all bottles and bisacodyl at the next follow up visit.

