4.2.6. Visit 6 (Month 12 or Early Term) +/- 4 days

Subjects will return at Day 360 for their final clinic visit. Vital signs (see [section 4.1](#) for details) and ECGs will be recorded. A physical examination will be performed.

Study

Braintree Laboratories, Inc.
Protocol Number BLI400-303

Confidential

personnel will weigh returned bottles and count bisacodyl for accountability purposes. Subjects will be queried for any adverse events or changes to their concomitant medications. Subjects will complete the PAC-QOL and PAC-SYM questionnaires. Samples for chemistry, hematology and urinalysis will be repeated as outlined in [Section 4.1](#). Clinically significant laboratory abnormalities present at Visit 6 should be followed until resolved or are considered stable.

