5. ADVERSE EVENTS

5.1. Adverse Event Definition and Reporting

An Adverse Event (AE) is any untoward medical occurrence associated with the use of a drug in humans, whether or not considered drug related. An AE can therefore be any unfavorable and unintended sign (including a clinically significant abnormal laboratory finding), symptom, or disease temporally associated with the use of a medicinal (investigational) product.

Adverse event collection will coincide with the subject providing informed consent to participate in the study and will conclude with the end of study participation at Day 374 Follow-up Call. Diarrhea should be reported as an adverse event if a subject has more than 3 watery stools per day. Subjects with clinically significant laboratory results at Visit 6 which are classified by the Investigator as adverse events should return for a repeat blood draw. Subjects will be instructed to report promptly adverse events to the Investigator. The Investigator will record date/time of report, date/time of onset, description of the adverse event, severity of adverse event, action(s) taken regarding treatment of the event, action(s) taken regarding study participation, duration of adverse event, and the Investigator's assessment of relationship of adverse event to study treatment.

The Investigator should assess the severity of each adverse event using the following categories:

Grade	Severity	Description
1	Mild	Barely noticeable, does not influence functioning Causing no limitations of usual activities
2	Moderate	Makes participant uncomfortable, influences functioning Causing some limitations of usual activities
3	Severe	Severe discomfort, treatment needed Severe and undesirable, causing inability to carry out usual activities
4	Life threatening	Immediate risk of death Life threatening or disabling
5	Fatal	Causes death of the participant

Braintree Laboratories, Inc.
Protocol Number BLI400-303

Confidential

The Investigator should assess the relationship to study drug for each adverse event using the following categories:

Categories of Attribution:	Description
UNRELATED	There is no evidence of any causal relationship.
POSSIBLE	There is some evidence to suggest a causal relationship (e.g., the event occurred within a reasonable time after administration of the trial medication). However, the influence of other factors may have contributed to the event (e.g., the patient's clinical condition, other concomitant events).

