9. DATA ANALYSIS

9.1. Sample Size

Consistent with *ICH E1A Guideline for Industry, the Extent of Population Exposure to Assess Clinical Safety: for Drugs Intended for Long-term Treatment of Non-Life-Threatening Conditions (March 1995)*, 300 subjects will be treated with BLI400 for 12 months. This will allow for detection of adverse events that may increase in frequency or severity over time.

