9.3.2. Safety Analyses

Analysis of safety will be performed using the modified Intent to Treat population (see [Section 9.4](#)).

Adverse Events

Adverse Events will be coded using the MedDRA classification to provide a preferred term and primary system organ class for each event. Proportions of subjects with adverse events will be presented for the overall study population, and each demographic subgroup (age, gender and race). Tables of AEs will be presented by system organ class and preferred term, and include overall totals for AEs within each system organ class. Counting will be done by subject and not by event. A table of counts and percentages will also be made of those subjects with SAEs or AEs which led to withdrawal from the study.

Treatment-emergent AEs are defined as adverse events that had an onset day and time on or after the day and time of the first dose of study drug until the Day 374 Follow-up Call. Adverse Events having missing onset dates will be considered as treatment emergent.

The difference in adverse event rates between study periods will be tested by Chi-Square or Fisher's exact test with 95% confidence intervals.

Laboratory Parameters

Summary statistics (i.e., mean, minimum, maximum, standard deviation, and number of subjects) will be presented for each laboratory parameter at each visit. Laboratory data will be summarized for the overall population and the elderly and non-elderly subgroups. When calculating the summary statistics only, the last observation within a visit window will be used if there are multiple observations. Changes from baseline (Visit 1) will be presented in a similar format. An additional listing will be provided of those subjects who have clinically significant laboratory values. The data will also be presented as shift tables and clinically significant abnormalities will be examined.

Results of laboratory tests for the change from baseline (Visit 1) and group differences will be tested using ANOVA.

Vital Signs

Summary statistics (i.e., mean, minimum, maximum, standard deviation, and number of subjects) will be presented for each vital sign at each visit and compared to the values obtained at Visit 1. When calculating the summary statistics only, the last observation within a visit window will be used if there are multiple observations. The data will also be presented as shift tables and clinically significant abnormalities will be examined.

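### The between-period AE test in 9.3.2 ignores that ECGs and physical examinations are scheduled unevenly, so silent findings from those tests can gather in the last period at a constant true rate

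*Combined protocol and SAP*

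**What the plan says.** The Adverse Events part of section 9.3.2 states: "The difference in adverse event rates between study periods will be tested by Chi-Square" or Fisher's exact test, with 95% confidence intervals. It excludes no type of AE and does not adjust for how often subjects are examined. The study periods are not defined.

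Section 5.1 lets an AE be "any unfavorable and unintended sign (including a clinically significant abnormal laboratory finding", so a new ECG or examination abnormality can enter the test. The investigator records the date of report and the date of onset separately. No rule says how to date the onset of a silent finding first seen on a scheduled test.

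The schedule is in sections 4.2.2 to 4.2.6 and the table in 4.3:

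- ECG on treatment: Visit 2 (vital signs "and ECGs will be recorded") and Visit 6, which is also the early-termination visit.
- Physical examination on treatment: Visit 6 or early termination only ("and ECGs will be recorded. A physical examination will be performed").
- Laboratory tests, vital signs and AE queries: every clinic visit (Months 2, 4, 6, 9 and 12).

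Section 9.1 says that "300 subjects will be treated with BLI400 for 12 months" and adds: "This will allow for detection of adverse events that may increase in frequency or severity over time".

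**The concern.** A between-period test assumes that an event has a similar chance of being recorded whichever period it occurs in. That holds for symptoms, which are queried at every clinic visit. It does not hold for a silent abnormality that only an ECG or a physical examination would reveal. In a subject who completes the study, the Month 12 ECG picks up whatever has developed and persisted over the preceding 300 days, and the Month 2 ECG only 60 days. The Month 12 examination is the first since baseline.

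Adjusting for period length does not remove this, because the relevant exposure is the time since the previous test. The period comparison is the planned AE test that bears on the stated aim of detecting events that increase over time, and there is no control arm. In the affected system organ classes or preferred terms, the schedule alone could look like that increase.

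**Working it through.** **No figure to reproduce.** Section 9.1 gives no event rate, power or alpha for the 300 subjects.

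**Inputs from the documents.** N = 300; visits at Days 60, 120, 180, 270 and 360; ECG at Days 60 and 360; examination at Day 360. The two-sided 0.05 level is inferred from "Fisher's exact test with 95% confidence intervals".

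**Assumptions not in the documents.** Constant hazard; finding silent, persistent and dated when detected; 360-day risk p of 1%, 3% or 5%; no dropout at first.

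**Expected ECG counts.** With λ = -ln(1 - p)/360:

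- found at Visit 2: 300 × [1 - exp(-60λ)]
- found at Visit 6: 300 × [exp(-60λ) - exp(-360λ)]

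At p = 3%, λ = 0.0000846 per day. Visit 2 finds 300 × 0.00506 = 1.5 and Visit 6 finds 300 × 0.02494 = 7.5.

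| p = 3% | Month 0-2 | 2-4 | 4-6 | 6-9 | 9-12 |
|---|---|---|---|---|---|
| True onsets | 1.5 | 1.5 | 1.5 | 2.2 | 2.2 |
| ECG-detected | 1.5 | 0 | 0 | 0 | 7.5 |
| Examination-detected | 0 | 0 | 0 | 0 | 9.0 |

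The last interval holds 7.5/9.0 = 83% of ECG findings, against a true share of 2.2/9.0, about 25%.

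**Fisher rejection, these findings tested alone.** Binomial counts were enumerated with 300 per period, treating periods as independent as the planned test does.

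| Annual risk | ECG, last vs first interval | ECG, last vs Month 6-9 |
|---|---|---|
| 1% | 3% | 4% |
| 3% | 39% | 76% |
| 5% | 68% | 99% |

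With true onset dates known, both ECG comparisons reject in under 1% of trials at 3% a year. Examination-only findings at 3% a year, last against any earlier interval, reject in 89%.

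**Other period definitions and dropout.** Months 0-6 against 6-12 were simulated with annual hazards of 3%, 5% and 10%:

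- No dropout, ECG: chi-square rejects in 50%, 74% and 97%; Fisher in 38%, 67% and 94%. Examination findings: chi-square 98-100%.
- 40% dropout (assumed) with ECG and examination at early termination: chi-square 39%, 66% and 88% for ECG, and 81-100% for examination.
- Even ascertainment: chi-square 4-7%.

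**If ECG findings are brief.** For durations of one month or less, ECG findings split about evenly between Months 2 and 12 (44% in the last half) and the test rejects in 4-7%. Examination findings still all appear at Month 12 when there is no dropout.

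**All-AE comparison.** Assume 10-31% of subjects per half-year have a symptomatic AE at a constant rate, and add the 3% ECG artefact. At a 10% background the halves become 1 - 0.90 × (1 - 0.00506) = 10.5% and 1 - 0.90 × (1 - 0.02494) = 12.2%. Over the background range Fisher rejects in 5-8% and chi-square in about 6-11%. At 1% a year the figures are about 4% and 5-6%. Larger inputs move it further: Fisher gives 8-17% for ECG at 5% a year, and 7-15% for examination findings at 3% a year.

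**The case against.** The strongest reply is that the high rejection rates describe a test of ECG- or examination-detected events taken alone, and 9.3.2 plans no such class. Its tables are overall, by system organ class and by preferred term. This stands: a reader might infer that the overall AE comparison will show a false late rise, and at the lower assumed rates it hardly moves.

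The assumed rates also lack support in the documents. The introduction expects AEs to be largely gastrointestinal, and clinically significant ECG abnormalities are excluded at entry. At 1% a year the ECG comparison rejects less often than the nominal 5%. This stands too, so the result has to be read as a range.

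Three further points hold in part:

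- **Early termination.** A reader might infer that nothing can be detected by ECG or examination at Months 4, 6 and 9. Early-termination visits include both tests, so this is true only without dropout. They weaken the pile-up but do not remove it.
- **Onset dating.** Onset is recorded separately from report, so dating at detection is an assumption. For a silent finding, though, the plan offers no other rule.
- **Existing ECG analysis.** Section 9.3.2 analyses ECG variables by visit. That covers the measurements and does not correct the AE test.

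A reader might also infer an opposite bias for laboratory events, from three draws in the first half and two in the second. That needs brief abnormalities with a fixed risk per draw, a different model from the persistent one used for ECG. Even then, a 1% risk per draw gives 3.0% against 2.0%, which Fisher's test flags in about 7% of trials. Persistent laboratory findings are balanced between halves.

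**Conclusion.** The concern holds for AEs first identified at a scheduled ECG or physical examination. The schedule and the absence of any allowance for it are plain in the documents. The direction is the same for visit intervals and for halves of the study.

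The size depends on undefined periods and assumed rates: negligible for ECG findings at 1% a year, and large at 3-5% a year when those findings are tested alone. The ECG part needs silent, persistent findings dated at detection. The examination part does not need persistence.

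The documents do not support a claim that the overall AE comparison is invalid, because symptoms are queried at every clinic visit and the all-AE test shifts far less than the affected categories. Nor do they support excluding laboratory-detected events. This is a point to correct in the analysis text, and the trial's procedures can stay as they are.

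**What to change.** In section 9.3.2:

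1. Add an AE flag for events first identified at a scheduled ECG or physical examination.
2. Run the between-period AE test on events without that flag, and keep the all-AE version as a secondary display. Laboratory-detected events stay in.
3. Report flagged ECG and examination findings as the proportion newly abnormal among subjects tested at each scheduled assessment (Visit 2, Visit 6, early termination), stating the time since the previous assessment.
4. Label any person-time rate as assuming persistent findings. Under that assumption the 3% example gives 1.52/(300 × 60) = 8.4 and 7.48/(300 × 300) = 8.3 per 100,000 days. For brief findings with equal risk per test, the same division would create a false five-fold decline (300/60).

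The cost is one paragraph, one extra flag to collect and one small table, and the between-period test covers slightly fewer events. No visit or procedure changes.

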3.2. Number of Subjects

Approximately 300 constipated subjects will be enrolled into this study, including approximately 100 elderly subjects (≥ 65 years of age at Visit 1).

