3.3. Duration of Study

Qualifying subjects will receive BLI400 at Visit 1 and will begin a 12-month Treatment Period. Subjects will return for clinic visits at the end of Months 2, 4, 6, 9 and 12. A follow up call will take place 2 weeks after the end of treatment. A completed subject is defined as a subject that completes the Visit 6 (Month 12) visit.

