9.4.1. Modified Intention-to-Treat (mITT) Population

This population consists of all enrolled subjects that took at least one dose of study medication. This population will be utilized for all safety analyses.

9.4.2. **Per-Protocol Population**

The per-protocol (PP) population will consist of all subjects in the mITT population who have not violated study entry criteria and have not deviated significantly from the protocol during the course of the study. Any analyses from this population will be considered as supportive to the ITT and mITT analyses. Reasons for exclusion from the PP population will be defined in the clinical study report.

10. **DRUG INVENTORY AND DISPOSITION**

At the conclusion of the study, all drug materials will be accounted for. Federal law requires that, at the conclusion of the study, all drug materials must be returned to the study sponsor or destroyed according to local regulations.

11. **STUDY MONITORING**

A Braintree Laboratories Study Monitor or qualified designee will visit the study center prior to the commencement of the study and periodically during the course of the study in accordance with federal guidelines governing the sponsorship of studies.

12. **DOCUMENTS AND NOTIFICATIONS**

12.1. **Informed Consent**

Written informed consent will be obtained from the subjects by the Investigator and will be kept on file at the study center. Documentation of the consent process should be noted in the study source documents.

12.2. **Institutional Review Board**

Peer review and approval of the protocol by an appropriate Institutional Review Board is required prior to commencement of enrollment. Amendments to the approved protocol must also be submitted to the Institutional Review Board and approved prior to their implementation.

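### AE rates over time are compared with a test that ignores the order of the study periods; if these are the five visit intervals, this costs about 11–22 points of power against a steady rise

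*Combined protocol and SAP*

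**What the plan says.** Section 9.1 takes the number from an exposure guideline: "300 subjects will be treated with BLI400 for 12 months". It then says what that number is good for: "This will allow for detection of adverse events that may increase in frequency or severity over time". It attaches no power, significance level, AE rate or size of increase. Section 3.2 gives about the same number as enrolled: "Approximately 300 constipated subjects will be enrolled into this study, including approximately 100 elderly subjects".

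For adverse events over time, Section 9.3.2 plans one inferential analysis: "The difference in adverse event rates between study periods will be tested by Chi-Square or Fisher's exact test with 95% confidence intervals". Section 9.2 otherwise describes treatment-emergent rates as a descriptive presentation. Section 9 contains no trend test for adverse events and no other AE analysis that uses time order.

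The plan does not say what the study periods are. Section 3.3 names a single one: "Qualifying subjects will receive BLI400 at Visit 1 and will begin a 12-month Treatment Period". The nearest thing to a division of it is the visit schedule in the same section: "Subjects will return for clinic visits at the end of Months 2, 4, 6, 9 and 12". Safety is analysed in the mITT set of Section 9.4.1: "This population consists of all enrolled subjects that took at least one dose of study medication". One subject can therefore contribute to every period.

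Onset times are collected. Section 5.1 states: "The Investigator will record date/time of report, date/time of onset, description of the adverse event".

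**The concern.** A rise in adverse events with longer use is a directional question about an ordered factor. With three or more periods, Pearson's chi-square and Fisher's exact test give the same p-value if the periods are shuffled. A steady climb counts for no more than an erratic pattern of the same size, and the evidence is spread over K−1 degrees of freedom. A significant overall result does not by itself say that the rate went up.

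The same people are also counted in each period, while both tests assume independent groups.

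This is a single-arm study, so change over time is one of the few comparisons it can make. A non-significant result from a test with little sensitivity to a steady rise could be reported as no increase with chronic use.

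**Working it through.** **No figure to reproduce.** The 300 rests on exposure, not on a power calculation. Everything below is therefore illustrative.

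**Inputs.** From the documents: 300 subjects (9.1), and visits at Months 2, 4, 6, 9 and 12 (3.3), scheduled at Days 60, 120, 180, 270 and 360 (4.2). Assumed: the periods are the five visit intervals, of about 60, 60, 60, 90 and 90 days; two-sided 5%; all 300 subjects in every period; a linear rise in the proportion of subjects with an event.

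**Formula.** For K equal, independent periods with n subjects each, the noncentrality is λ = n Σ(pᵢ − p̄)² / [p̄(1 − p̄)]. Under a linear rise the trend test has the same λ. Only the degrees of freedom differ: the critical value is 9.488 on 4 df for the unordered test and 3.841 on 1 df for the trend test. Power is the noncentral chi-square tail beyond that value.

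**Example, 5% to 10% over five periods.** The deviations from 7.5% are ±2.5, ±1.25 and 0 points. The sum of squares is 2 × (0.025² + 0.0125²) = 0.0015625, so λ = 300 × 0.0015625 / (0.075 × 0.925) = 6.76. Power is 52% unordered and 74% for trend.

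| Rise | Five equal periods: unordered / trend | 60/60/60/90/90 days with length offset (rates per 60 days): unordered / trend |
|---|---|---|
| 2% to 4% | 21% / 36% | 24% / 41% |
| 3% to 6% | 31% / 51% | 36% / 56% |
| 5% to 10% | 52% / 74% | 57% / 78% |
| 10% to 15% | 34% / 54% | 36% / 57% |

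**Number of periods.** The table gives the loss over the range where the trend test has 30% to 95% power.

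| Periods | Points lost by the unordered test |
|---|---|
| 2 | 0 |
| 3 | 4–10 |
| 4 | 8–17 |
| 5 | 11–22 (maximum 21.8) |

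With two periods the 2×2 chi-square already has 1 df, so nothing is lost. Outside that power range the loss is smaller: for 10% to 20% over five periods it is 88% against 97%.

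**Same subjects in each period.** In a simulation with five periods and within-subject correlation 0.3 on the latent scale, both tests were made paired (Cochran's Q against a paired linear contrast). For the four rises in the table, power was 22.2/38.5, 32.3/54.7, 57.9/78.7 and 38.4/60.7%, a gap of about 16 to 22 points. So the loss from ignoring order remains once pairing is dealt with. Separately, at a flat 10% rate the planned unpaired test rejected in 2.8%, 1.4% and 0.3% of runs at correlations 0.3, 0.5 and 0.7, so it is conservative.

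**Unequal lengths.** A constant hazard giving 10% per 60 days gives 1 − 0.9^1.5 = 14.6% per 90 days. Comparing raw proportions would then declare a difference in about 56% of trials with the planned test, and in about 65% with a naive trend test, although the hazard is flat. A trend test without a person-time offset would not be a safe replacement.

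**Where the trend test does worse.** For 5, 5, 5, 5, 10%, p̄ = 6%. Unordered: λ = 300 × (4 × 0.01² + 0.04²) / 0.0564 = 10.64, power 75%. Trend, with scores −2 to 2: λ = 300 × 0.10² / (10 × 0.0564) = 5.32, power 64%. For the U-shape 15, 10, 8, 10, 15% the figures are 80% against 5%.

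**The case against.** Four points can be made for the plan.

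1. The loss hangs on an undefined term. With two periods there is none. This stands, and is why the size can only be given under a stated assumption and why the periods need defining first.

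2. The mention of 95% confidence intervals suggests differences between pairs of periods, which carry a sign. First against last, with 300 in each, has power 30, 43, 64 and 46% in the four scenarios, against 36, 51, 74 and 54% for trend: a gap of only 6 to 10 points. This is a fair reading. But the plan does not say which pairs, and five periods give 5 × 4 / 2 = 10 of them with no rule for reading them together.

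3. A linear rise is the pattern that suits the proposed test, and Section 9.1 does not say linear. A late rise confined to the last period, though monotone, is found better by the unordered test. This stands, and is the reason to keep the between-period comparison.

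4. A reader might infer that the trial was sized to detect a rise and now falls short of its planned power. The documents do not support that: the 300 comes from exposure, with no power stated.

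A reader might also put the loss as high as 27 points. That gap appears when two independence-based tests are run on correlated data (27.8% against 54.4% for 10% to 15% at correlation 0.3). It mixes in the conservatism caused by repeated subjects. With both tests paired, the same scenario gives about 22 points.

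**Conclusion.** The mismatch is real. The sample is said to allow detection of events that increase over time, but the only inferential analysis over time is blind to time order when there are three or more periods, and it treats repeated observations on the same subjects as independent.

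The size is conditional: about 11 to 22 points of power for five visit intervals, 300 subjects per period, two-sided 5%, a roughly linear rise, and effects for which the trend test has 30% to 95% power. With fewer periods it shrinks, to nothing at two. The AE rates, the significance level and the correlation are assumptions, because the documents give none. The simulated figures carry about 1 to 2 points of Monte Carlo error.

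It would be too strong to say that the planned test misses a power target, or that a trend test is better for every kind of increase. This is a worthwhile improvement at low cost. It concerns the frequency of events; Section 9.1 also mentions severity, which these calculations do not address.

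**What to change.** In Section 9.3.2:

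- Define the study periods as the visit intervals (0–2, 2–4, 4–6, 6–9 and 9–12 months). State how events with onset after Visit 6 and events with missing onset dates are assigned, since both count as treatment-emergent.
- Make the main analysis of AE rates over time a 1-df trend test from a log-link model of AE occurrence by subject and period, with time on treatment as a linear term, a log person-time offset and a within-subject (GEE or robust) variance.
- Report the rate ratio, for example per 3 months, with its 95% confidence interval: overall, by system organ class, and for preferred terms frequent enough to fit, with the frequency threshold set in advance. Label term-level results exploratory.
- Keep the between-period comparison alongside it, for late-onset and non-monotone patterns.

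The cost is a short paragraph and one model per term. No new data are needed, since onset times are already collected. Sparse terms may not fit, hence the threshold. The linear term gives up some power for a rise confined to the last period, which the retained comparison covers. The offset allows for shortened follow-up but does not remove bias if subjects leave because of adverse events.

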9.3.2. Safety Analyses

Analysis of safety will be performed using the modified Intent to Treat population (see Section 9.4).

Adverse Events

Adverse Events will be coded using the MedDRA classification to provide a preferred term and primary system organ class for each event. Proportions of subjects with adverse events will be presented for the overall study population, and each demographic subgroup (age, gender and race). Tables of AEs will be presented by system organ class and preferred term, and include overall totals for AEs within each system organ class. Counting will be done by subject and not by event. A table of counts and percentages will also be made of those subjects with SAEs or AEs which led to withdrawal from the study.

Treatment-emergent AEs are defined as adverse events that had an onset day and time on or after the day and time of the first dose of study drug until the Day 374 Follow-up Call. Adverse Events having missing onset dates will be considered as treatment emergent.

The difference in adverse event rates between study periods will be tested by Chi-Square or Fisher's exact test with 95% confidence intervals.

Laboratory Parameters

Summary statistics (i.e., mean, minimum, maximum, standard deviation, and number of subjects) will be presented for each laboratory parameter at each visit. Laboratory data will be summarized for the overall population and the elderly and non-elderly subgroups. When calculating the summary statistics only, the last observation within a visit window will be used if there are multiple observations. Changes from baseline (Visit 1) will be presented in a similar format. An additional listing will be provided of those subjects who have clinically significant laboratory values. The data will also be presented as shift tables and clinically significant abnormalities will be examined.

Results of laboratory tests for the change from baseline (Visit 1) and group differences will be tested using ANOVA.

Vital Signs

Summary statistics (i.e., mean, minimum, maximum, standard deviation, and number of subjects) will be presented for each vital sign at each visit and compared to the values obtained at Visit 1. When calculating the summary statistics only, the last observation within a visit window will be used if there are multiple observations. The data will also be presented as shift tables and clinically significant abnormalities will be examined.

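### A Visit 6 repeat draw triggered by an abnormal result displaces the scheduled end-of-treatment value in the laboratory summary tables whenever it falls in the visit window, which is not defined for analysis

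*Combined protocol and SAP*

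**What the plan says.** Section 9.3.2 (Laboratory Parameters) plans by-visit tables: "Summary statistics (i.e., mean, minimum, maximum, standard deviation, and number of subjects) will be presented for each laboratory parameter at each visit". For a visit with more than one value it sets this rule: "When calculating the summary statistics only, the last observation within a visit window will be used if there are multiple observations". It continues: "Changes from baseline (Visit 1) will be presented in a similar format". The change from baseline is also to be tested by ANOVA. Two further displays are planned: "An additional listing will be provided of those subjects who have clinically significant laboratory values", and "The data will also be presented as shift tables and clinically significant abnormalities will be examined". The multiple-observation sentence appears again, word for word, for vital signs.

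Two other sections generate a second laboratory value. Section 5.1 says that subjects whose Visit 6 results are clinically significant and are recorded by the Investigator as adverse events "should return for a repeat blood draw". Section 4.2.6 adds: "Clinically significant laboratory abnormalities present at Visit 6 should be followed until resolved or are considered stable".

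The Clinical Protocol Summary Sheet makes the comparison of chemistry, hematology and urinalysis with baseline part of the primary endpoint.

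**The concern.** A last-value rule does no harm when duplicate samples arise for reasons unrelated to the result. At Visit 6 the prescribed reason for a second sample is that the first was abnormal. The follow-up is designed to run until the finding has gone or settled, and by then the subject is off drug. If that second sample is the one kept, the 12-month table loses an on-drug abnormal value and gains an off-drug recheck, in just those subjects who had something to report.

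The study exists to describe safety under chronic use, and Visit 6 is its only 12-month laboratory time point. The minimum and maximum columns, which are there to show outliers, would be affected most. The mean and the change from baseline would be pulled toward no change.

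**Working it through.** The plan states no figure that depends on this rule. The sample size of 300 (Section 9.1) rests on an exposure guideline, not a power calculation, so there is nothing to reproduce first.

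**1. Is the Visit 6 repeat taken after treatment?** Bottles dispensed: 2 at Visit 1 (Section 4.1), 2 at Visit 2 (4.2.2), 2 at Visit 3 (4.2.3), 3 at Visit 4 (4.2.4) and 3 at Visit 5 (4.2.5). Each holds 30 days of dosing (3.4).

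- 2 + 2 + 2 + 3 + 3 = 12 bottles; 12 × 30 = 360 days, which matches the Day 360 visit.
- Section 4.2.5 has all bottles returned at Visit 6, and the table in Section 4.3 marks no dispensing there.

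So a draw after Visit 6 is a post-treatment draw.

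**2. When does the repeat fall in the window?** No analysis window is defined. The ±4 days are acceptable deviations from the visit schedule (Section 4). Assume, for illustration, that they also serve as the analysis window: 360 ± 4 gives Days 356 to 364, nine allowed visit days. A repeat L days after a visit on day v stays inside if v + L ≤ 364, so the number of qualifying visit days is 9 − L (zero for L ≥ 9).

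| Days from visit to repeat (L) | Visit days with the repeat in the window | Affects an on-time Day 360 visit? |
|---|---|---|
| 1 | 8/9 | yes |
| 3 | 6/9 | yes |
| 5 | 4/9 | no |
| 7 | 2/9 | no |
| 9 or more | 0/9 | no |

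For a Day 360 visit the repeat must come within 4 days. With an open-ended window, every repeat would displace the scheduled value. Visit 6 is also the early-termination visit. That visit has no target day, so the tolerance sets no limits for it.

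**3. Which way does the replacement push?** The prescribed repeat follows an abnormal Visit 6 result, and none is prescribed after a normal one. The second value tends to be closer to normal through regression to the mean, loss of any drug effect, and follow-up that ends at resolution or stability.

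**4. How large could it be?** The documents give no variances or abnormality rates, so this is illustration only. Assumptions: 300 subjects; values in SD units; 2% (6 subjects) with a true on-drug shift of +3 SD; a repeat for every value above a threshold of 2.0 to 3.0 SD; correlation of 0.5 to 0.7 between first and repeat values; drug effect gone at the repeat; 2,000 simulated trials per setting.

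| Share of repeats in the window | Expected Visit 6 maximum (SD) | Expected Visit 6 mean (SD) |
|---|---|---|
| Scheduled value kept | about 4.3 | about +0.06 |
| 22% (about 2/9) | about 4.1 | +0.04 to +0.05 |
| 67% (about 6/9) | 3.5 to 3.6 | +0.01 to +0.04 |
| 100% | 2.4 to 2.8 | −0.02 to +0.03 |

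The simulated trigger is a simple threshold. The plan's trigger also needs the Investigator to judge the result clinically significant and record it as an adverse event, so fewer values may be redrawn than assumed here.

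**The case against.** The strongest reply is that the problem is narrow and the abnormal value is kept elsewhere. Most of that stands.

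- **The repeat does not always replace the first value.** A reader might infer that it does. It does so only inside a window that the plan leaves undefined. Under the ±4-day assumption, an on-time subject is affected only if the central laboratory result, the clinical judgement, the adverse event classification and the return visit all fit within 4 days.
- **Visits 2 to 5 and vital signs.** It is tempting to extend the bias to these because the rule covers them. The documents prescribe no repeat triggered by an abnormality there, so the effect would depend on unscheduled measurements that the protocol does not describe.
- **Not every duplicate is selected for abnormality.** After a washout, Section 4.1 has the Visit 1 procedures repeated apart from consent, whatever the first results were. Keeping the last pre-dose value is reasonable there.
- **The signal is not lost.** The rule covers summary statistics only. The listing of clinically significant values should still show the result, and every finding that triggers the Section 5.1 repeat is by definition already an adverse event.
- **The displays need not conflict.** One might conclude that the shift tables and the summary tables will disagree. The plan does not say which record feeds the shift tables or the ANOVA, so they may or may not.

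What the reply does not answer is that a listing does not correct a biased mean, minimum or maximum. The undefined window also leaves the size of that bias to a later programming choice.

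**Conclusion.** The concern holds for the Visit 6 laboratory summaries, on the condition that the repeat falls in the window. The rule then puts a post-treatment value, selected to be nearer normal, into the 12-month mean, minimum and maximum. That it also reaches the change from baseline is the natural reading of Section 9.3.2, not an explicit statement.

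The frequency cannot be known from the documents. The fractions from 8/9 down to 2/9 rest on treating the scheduling tolerance as the analysis window and counting each allowed day equally. The simulated sizes rest wholly on assumed values. They run from slight, when about a fifth of repeats are in the window, to a marked loss of the extremes when all are, and none should be quoted as this trial's bias. The rule is worth changing before analysis because the bias is one-sided, touches a primary endpoint component and is cheap to remove.

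**What to change.** Replace the multiple-observation sentence in Section 9.3.2, for laboratory data and, for consistency, vital signs, with wording such as:

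> For post-baseline visits, by-visit summaries, change from baseline and the ANOVA use the sample or measurement taken for the scheduled visit, including the scheduled Visit 6 or early-termination one. Unscheduled repeats are listed and do not replace it. Repeats taken after the Visit 6 or early-termination sample are shown separately as follow-up. A separate table gives the worst post-baseline value up to and including the scheduled Visit 6 or early-termination sample, counting unscheduled draws; the shift tables use this value. Baseline is the last value before the first dose.

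The cut-off should be the scheduled Visit 6 or early-termination sample, not the last dose. That sample may itself be drawn after the final dose: supply covers 360 days and the visit may fall as late as Day 364. A last-dose cut-off read literally could move the 12-month data into follow-up.

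The cost is wording, a programming rule and one more table, with no new visits or samples. Reported extremes may look slightly less favourable, and a spurious first value that the laboratory has not rejected would stay in the by-visit table, with its repeat visible in the listing.
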